2.8.2.1 Adverse events of special interest / grouping of AEs

Selected tables will be produced for Adverse Events of Special Interest (AESI) (i.e., risks) defined in the latest version of case retrieval sheet (eCRS) at the time of analysis implementation (i.e., study database lock).

The LMI070X2201 eCRS is available at <http://go/ecrs> by selecting either

- CRS NAME: (LMI070 Spinal muscular atrophy) or
- CRS ID: 3689
- Within the document, select SP="Y"

Specifically, incidence of TEAEs that fulfill the risk search terms as defined in eCRS will be summarized by risk name, level, study part and treatment group (for Parts 2 & 3 only) with crude incidences and 95% confidence intervals presented.

Similarly, separate summaries will be provided for serious TEAEs that fulfill the risk search terms as defined in eCRS. Additionally, incidence of any TEAEs that fulfill the search terms as defined in eCRS will also be summarized by risk name, level, and maximum CTCAE grade.

Bar charts of MedDRA preferred terms that fulfill the search terms as defined in eCRS will be produced for crude incidences by part.

2.8.3 Deaths

Deaths will be summarized by providing the number and percentage of subjects by study part. All deaths as recorded in the final database (i.e., up to database lock) will be included.

Additionally, time to death, permanent ventilation or tracheostomy will be displayed in a Kaplan-Meier plot along with the respective table (see [Section 2.7.2](#)).

2.8.4 Laboratory data

Data summaries will be provided in SI units. The summary of laboratory evaluations will be presented for three groups of laboratory tests: Hematology, Chemistry and Urinalysis. On presenting summary statistics, laboratory data will be grouped and displayed in an alphabetical order within each of the three groups.

Descriptive summary statistics (mean, median, standard deviation, Min and Max) of the change from baseline in the laboratory result to each study visit-window by treatment group will be presented for continuous variables. Change from baseline will only be summarized for subjects with both baseline and post baseline values and will be calculated as:

$$\text{change from baseline} = \text{post baseline value} - \text{baseline value}$$

In addition, shift tables will be provided for all parameters to compare a subject's baseline laboratory evaluation relative to the post-baseline values. For the shift tables, the normal local

laboratory ranges will be used to evaluate whether a particular laboratory test value was normal, low, or high relative to whether or not the baseline value was normal, low, or high. These summaries will be presented by laboratory test overall in Parts 1 & 3, additionally by actual treatment group in Parts 2 & 3. Shift table will also be provided for urinalysis results to compare baseline to post-baseline extreme values (negative, +, 2+, 3+, or 4+).

Number of subjects with newly occurring liver enzymes abnormalities will be summarized using the respective criteria. Newly occurring liver enzymes abnormalities are defined in [Section 5.3.2](#).

For both shift tables and newly occurring liver enzymes abnormalities, all applicable post-baseline values (including unscheduled or unplanned visits) will be checked against the respective criteria and the rules for handling multiple laboratory assessments within visit windows will not be applied.

For continuous variables databased as <lower limit, these will be imputed as being half of the lower limit.

The following graphs will be generated for liver enzymes:

- Panel plot of individual subjects for alkaline phosphatase, total bilirubin, ALT and AST with dose as background shading – one panel per subject (Parts 1 & 3 and Parts 2 & 3)
- eDISH scatterplot of Total Bilirubin and ALT on log-log axes (Parts 1 & 3); additionally stratified by treatment group (Parts 2 & 3)
- Matrix plot of each of the parameters (ALT, AST, Total Bilirubin and Alkaline Phosphatase) maximum post-baseline/ULN normalized (Parts 1 & 3, and Parts 2 & 3)

All above summaries include only data up to and including safety cut off. If there is any value for a parameter outside of the normal range for a subject, then all data of this parameter for that subject will be listed.

2.8.5 ECG and echocardiographic data

Clinically significant findings from ECG evaluations will be reported as AEs and included in the analysis of AEs. ECG parameters include max heart rate, mean PR duration, mean QT duration, mean QRS duration, QT_f (QT corrected using Fridericia's correction formula), and QT_b (corrected using Bazett's correction formula) - all as collected on the ECG CRF. Descriptive statistics of each ECG parameter will be provided overall (Parts 1 & 3) and by treatment group (Parts 2 & 3) for baseline and all relevant post-baseline visits.

The number and percentage of subjects meeting the criteria defined in [Table 2-15](#) will be provided for each criterion by treatment group for baseline and the relevant post-baseline assessments.

Table 2-15 Criteria for relevant ECG absolute values

Absolute values criteria:
QT > 450 msec
QTc > 450 msec

The number and percentage of subjects with echocardiography abnormality will be provided by treatment group for baseline and any time post-baseline.

All ECG data will be listed, and abnormalities will be flagged. For echocardiographic data, all patients with at least one abnormality will be listed.

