findings are new findings, cardiac effects are already listed as a risk in the current Investigator's Brochure (IB).

At the time this protocol amendment is written, three cases of cardiac SUSARs have been reported in the CLMI070X2201 study (see Section 1.1.1). The events consisted of PTs: left ventricular hypertrophy, sinus tachycardia, ejection fraction decreased (reported term: decreased systolic function of left ventricle EF45%), and hypertension, and pericardial effusion.

The SMN protein is expressed in moderate levels in skeletal as well as cardiac muscle (Coovert et al 1997). Multiple preclinical in vivo studies and emerging clinical findings in SMA patients suggest that partial deficiency state of SMN in SMA may have an adverse effect on cardiac embryogenesis and function. Cardiac deficits, including bradycardia, arrhythmias and impaired blood flow have been described in several mouse models of SMA and are often the cause of death of these mice (Heier et al 2010). Drug treatments that elevate SMN levels have been shown to improve heart function in the same models. (Heier and DiDonato 2015).

In patients, severe forms of SMA, including Type I SMA, have been associated with autonomic dysfunction, congenital heart block, ASD, VSD, aortic stenosis, hypoplastic aortic arch, severe aortic coarctation, partial atrioventricular canal, tricuspid atresia, a single ventricle and hypoplastic left heart syndrome (Bach 2007; Bach et al 2007; Menke et al 2008; Rudnik Schöneborn et al 2008; for review see also Shababi et al 2014).

In summary, there appears to be an association of structural cardiac disease and autonomic findings, presenting as bradycardia and heart rate variability abnormality, with severe SMA that could potentially cause, or contribute to, the findings seen in study CLMI070X2201.

The risk to patients will be minimized by safety monitoring for cardiovascular function including monitoring of blood pressure at regular visits, cardiac biomarkers, such as troponin and NTproBNP every 3 months, ECGs every 3 months and echocardiography performed every 6 months or when clinically significant elevation in troponin and or NTproBNP levels are identified by the investigators. It is important that investigators ensure these protocol required investigations and get early pediatric cardiology consult if any abnormalities are identified.

Additional risks

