7.4.6 Echocardiogram

An echocardiogram will be performed at the timepoints defined in the Assessment Schedule or if clinically significant elevation of Troponin and/or elevated NTproBNP (as unscheduled)in consultation with pediatric cardiologist (refer to Table 5-7). The following standard parameters will be obtained during the study:

- Biplane four and two chamber Left Ventricular End Diastolic Volume(LVEDV)
- Biplane four and two chamber Left Ventricular End Systolic Volume(LVESV)
- Left Ventricular Ejection Fraction from LVEDV and LVESV(LVEF)
- Left Ventricular Internal Dimension Diastole) 2-D guided M-mode measurements from parasternal long axis (LVIDd)
- Left Ventricular Internal Dimension Systole (LVIDs) 2-D guided M-mode measurements from parasternal long axis
- Left Ventricular Fractional Shortening (LVFS)
- Intraventricular Septum Thickness diastole (IVSTd) 2-D guided M-mode measurements from parasternal long axis
- Left Ventricular Posterior Wall Thickness diastole (LVPWTd) 2-D guided M-mode measurements from parasternal long axis
- tricuspid regurgitation(TR) peak velocity (continuous wave Doppler)
- Left Ventricular End Diastolic Volume Index(LVEDVI) = LVEDV/ BSA
- Left Ventricular End Systolic Volume Index(LVESVI) = LVESV/ BSA

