2.1.4 Issues resolved in the analysis datasets

2.1.4.1 ECG/ECHO data

For some patients, ECG/ECHO data was entered mistakenly as unscheduled visits instead of scheduled visits. The algorithms for multiple assessments for quantitative variables will be applied (see [Section 2.1.3](#)). For descriptive analyses for these patients, all data within each scheduled visit window will be taken into account, and the value on the closest day followed

by the worst case will be used. For worst case analyses, the worst case within a time window will be used.

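### SAP 2.8.5 specifies no quantitative echocardiography output, so a fall in LVEF that stays short of the undefined abnormality threshold appears in none of the planned echo outputs

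*SAP*

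**What the plan says.** Echocardiographic evaluation is among the primary safety endpoints for all three parts (protocol 2.1, SAP 1.1.1). Protocol 7.4.6 states that "The following standard parameters will be obtained during the study" and lists eleven numeric measures: LVEDV, LVESV, LVEF, LVIDd, LVIDs, LVFS, IVSTd, LVPWTd, tricuspid regurgitation peak velocity, LVEDVI and LVESVI.

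SAP 2.8.5 names two echo outputs:

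- a table: "The number and percentage of subjects with echocardiography abnormality will be provided by treatment group for baseline and any time post-baseline";
- a listing: "For echocardiographic data, all patients with at least one abnormality will be listed".

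Neither sentence says what counts as an abnormality, or whether the listing shows measured values or only the flag. For ECG the same section is fuller: "Descriptive statistics of each ECG parameter will be provided overall (Parts 1 & 3) and by treatment group (Parts 2 & 3"), at baseline and the relevant later visits, with numeric QT criteria as well.

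SAP 2.1.4.1 reports a data problem: "For some patients, ECG/ECHO data was entered mistakenly as unscheduled visits instead of scheduled visits". It resolves this with the rules for quantitative variables, and refers to descriptive analyses by visit window and to worst-case analyses.

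**The concern.** Protocol 3.8 (Cardiac effects) records three cardiac SUSAR cases. Their terms include left ventricular hypertrophy and an ejection fraction decrease to 45%. Amendment 11 was prompted mainly by cardiomyocyte vacuolation in mice. LVEF and wall thickness measure the quantities at issue, yet the SAP specifies no numerical output for either.

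A yes/no count over all post-baseline echoes has three weaknesses:

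- It does not register a decline that stops short of the threshold.
- It does not link a child's later result to that child's baseline, so it cannot show worsening in a child already abnormal at the start.
- It has no time axis, and its expected value rises with the number of echoes.

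At stake is whether the final report can show a gradual cardiac change in a first-in-human infant study.

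**Working it through.** **Step 1: outputs specified for each safety domain**

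| Domain (SAP section) | By-visit values or change | Shift table or numeric criteria | Individual plots |
|---|---|---|---|
| Laboratory (2.8.4) | yes | yes | yes, liver tests, dose shading |
| ECG (2.8.5) | yes | yes, QT and QTc above 450 msec | none named |
| Vital signs (2.8.6) | yes | yes | yes |
| Neurophysiology (2.8.8) | descriptive summary, visits not stated | none named | yes, Parts 2 & 3 |
| Echo (2.8.5) | none named | none; abnormality count only | none named |

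Protocol 11.5.2 does not fill the gap. It covers adverse events, vital signs, ECG and laboratory data, and does not mention echo.

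**Step 2: SAP 2.1.4.1 against SAP 2.8.5**

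Section 2.1.4.1 selects the closest value in a window, then the worst. That presupposes an output that uses echo values by visit. Section 2.8.5 names none, and the worst-case direction table in SAP 2.1.3 has no echo row. The two sections do not fit together.

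**Step 3: illustration of the information lost**

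There is no figure in the plan to reproduce. The documents give no LVEF mean, SD or limit, so every LVEF value here is an assumption: baseline mean 65%, SD 5, lower limit 55%. The sample is the 25 Part 2 children with both doses pooled.

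*Flagged at one post-baseline echo after a mean fall of d points:* share = Φ((55 − 65 + d)/5). With no fall it is Φ(−2) = 0.023, or 0.6 of 25 children.

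*Paired change from baseline:* power of a two-sided 5% paired t-test from the noncentral t with 24 df and noncentrality (d/SD of change) × √25. SD of change is taken as 4, 5 and 7. Since SD of change² = 2 × 25 × (1 − ρ), the ends 4 and 7 correspond to within-child correlations of 1 − 16/50 = 0.68 and 1 − 49/50 = 0.02. No test is planned; power serves only to measure information.

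| Mean fall d | Share flagged | Expected of 25 | Not flagged | Power, SD 4 | Power, SD 5 | Power, SD 7 |
|---|---|---|---|---|---|---|
| 3 | 0.081 | 2.0 | 92% | 0.95 | 0.82 | 0.54 |
| 5 | 0.159 | 4.0 | 84% | >0.99 | >0.99 | 0.93 |
| 7 | 0.274 | 6.9 | 73% | >0.99 | >0.99 | >0.99 |

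**Step 4: effect of repeated echoes**

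Suppose there is no decline and the chance of a flag is 0.023 per echo. If echoes were independent, the chance of ever being flagged would be 1 − (1 − 0.023)^k:

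- k = 4: 0.089, or 25 × 0.089 = 2.2 children;
- k = 8: 0.170, or 25 × 0.170 = 4.2 children.

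Independence is the extreme case; with perfectly correlated echoes the expected count stays at 0.6. Within that range, repetition alone can produce about the count (4.0) that a true 5-point fall gives at a single echo. The baseline column rests on one reading, so the two columns are not comparable.

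**The case against.** The strongest reply is that the SAP does not ignore echo values. Section 2.1.4.1 foresees descriptive and worst-case handling. Section 2.8.5 lists flagged patients. The introduction to 2.8 sends clinically significant findings to the adverse-event analysis and says that all safety assessments are summarized or listed as appropriate. Section 2.8.2.1 adds tables for risks defined in a retrieval sheet that is not part of the documents. The study is non-confirmatory, and protocol 11.5.2 promised no echo analysis.

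Much of this stands, and it rules out several stronger readings that a reader might infer:

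- *Echo values will never be analysed, or a decline cannot be seen at all.* Not supported. Quantitative handling is foreseen, and a decline in a flagged child may be visible if the listing shows values.
- *Baseline is ignored.* Not so: the count is given at baseline too. What is missing is pairing within a child.
- *The count would miss even a very large fall.* Under the SD of 5 and limit of 55% used above, a fall in mean LVEF from 70% to 56% would flag Φ(−0.2) = 42%, about 16 of the 38 treated children, at one echo.
- *Every child has a baseline echo and a full set of values.* Not established. The Amendment 03 log describes echo as newly added when nine patients had been treated. Amendment 11 detailed the parameters in 7.4.6 only after patients had moved to Part 3.

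The reply does not close the gap. The listing excludes children never flagged. The adverse-event route depends on a finding being judged clinically significant, so it is also blind below a threshold. The general sentence in 2.8 can be met by the partial listing. Section 2.1.4.1 says how to choose a value, not which output uses it.

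**Conclusion.** The point holds as a gap in specification. Followed as written, 2.8.5 gives an undefined yes/no count and a listing of flagged patients. A decline below the threshold appears in neither, and no output pairs a child's echo values with baseline. Sections 2.1.4.1 and 2.8.5 are inconsistent on whether echo is analysed quantitatively.

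The size cannot be fixed from the documents. Under the assumed distribution, 73% to 92% of children stay unflagged at one echo after a mean fall of 7 to 3 points. A paired summary would detect those falls with power from 0.54 (3 points, SD of change 7) to above 0.99. The count therefore loses much of the information, but not all of it. These figures rest on normality, the assumed mean, SD and limit, pooling of the Part 2 doses, and a usable baseline echo in all 25 children. The textual finding depends on none of them. This is a worthwhile and inexpensive improvement; it does not invalidate the safety analysis.

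**What to change.** Reconcile SAP 2.1.4.1 with 2.8.5, add an echo row to the worst-case direction table in 2.1.3, and in 2.8.5:

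- define abnormality by its CRF field or by stated limits;
- summarise value and change from baseline by visit for LVEF, LVFS and the BSA-indexed volumes, in children with a pre-dose echo and at visits where values were recorded, with the number contributing shown;
- show IVSTd and LVPWTd descriptively, noting that raw changes include growth and that there is no control group;
- add individual panel plots with dose shading, as 2.8.4 already plans for liver tests;
- add a baseline-to-worst shift table;
- list all echo values, not only those of flagged patients.

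No fixed cut for an LVEF fall is proposed, because neither document gives a basis for one.

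The cost is SAP wording and descriptive programming, with no new assessments. First check which of the eleven measures are in the database for Part 1 and Part 2 visits. Some early Part 1 children may lack a baseline echo or recorded values and would then contribute only to the plots and listing, as far as their data allow.

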2.8.6 Vital signs

Vital sign measurements include sitting systolic and diastolic blood pressures, sitting pulse, body temperature, height and body weight.

Derivation of baselines for blood pressure and pulse are provided in [Section 2.1.1](#).

Height will be collected at screening visit only and will be summarized in the baseline characteristic summary only.

Analyses of vital sign measurements using descriptive summary statistics (mean, median, standard deviation, min, max) for the change from baseline for each post-baseline visit-window will be performed. These descriptive summaries will be presented by vital sign parameter and treatment group (Parts 2 & 3). Change from baseline will only be summarized for subjects with both baseline and post-baseline values and will be calculated as:

$$\text{change from baseline} = \text{post-baseline value} - \text{baseline value}$$

In addition, shift tables will be provided for all vital sign parameters to compare a subject's baseline value relative to the post-baseline values. For the shift tables, the reference ranges in [Table 2-16](#) will be used to evaluate whether a particular value was normal, low, or high relative to whether or not the baseline value was normal, low, or high.

Table 2-16 Reference ranges for vital sign parameters

Age window	Pulse rate	Systolic blood pressure	Diastolic blood pressure
0-<3 months	100-150	65-85	45-55
3-<6 months	90-120	70-90	50-65
6-<12 months	80-120	80-100	55-65
1-<3 years	70-110	90-105	55-70
3-<6 years	65-110	95-110	60-75
6-<12 years	60-95	100-120	60-75

Source: Nelsons textbook of Pediatrics 18th Edition

Apart from the growth measurement graphs mentioned in [Section 2.7.1](#), the following graph will be generated for vital signs data:

- Panel plot of individual vital signs over time – systolic and diastolic BP, and pulse

All above summaries include only data up to and including safety cut off. All vital signs data will be listed, and age-dependent abnormalities will be flagged

2.8.7 Ophthalmology Examination

All ophthalmological abnormalities will be descriptively summarized and for patients with at least one abnormality, data will be listed.

2.8.8 Neurophysiological Examination

All neurophysiological evaluations [Ulnar compound motor action potential (CMAP), Ulnar nerve conduction velocity (NCV), Sural SNAP, Sural sensory NCV] will be descriptively summarized and listed.

Furthermore the following analyses will be carried out:

- Spaghetti plot of raw neurophysiological parameters vs months from first dose over time with all raw data (Parts 2 & 3)
- Spaghetti plot of raw neurophysiological parameters vs months from first dose over time excluding implausible post-baseline zero values (Parts 2 & 3)
- Spaghetti plot on a log scale of raw neurophysiological parameters vs months from first dose over time excluding implausible post-baseline zero values (Parts 2 & 3)
- Spaghetti plot on a log scale of normalised neurophysiological parameters vs months from first dose over time with all normalised data (Parts 2 & 3)
- Spaghetti plot on a log scale of normalised neurophysiological parameters vs months from first dose over time excluding implausible post-baseline zero values (Parts 2 & 3)

2.8.9 Neurologic examination questionnaire

All data will summarized with appropriate descriptive statistics, and all data will be listed.

2.8.10 Acceptability and palatability questionnaire

All data will summarized with appropriate descriptive statistics.

2.9 Pharmacokinetic endpoints

[figure not shown]
Parts 1 & 3 and Parts 2 & 3

The following pharmacokinetic parameters will be analyzed: Cmax, Tmax, AUCtau or AUC0-168h, AUClast, AUCinf, T1/2, Vz/F and CL/F from the plasma concentration-time data.

Descriptive analyses

Branaplam plasma concentration data will be listed by study part, administered dose, subject, and sampling time point. Descriptive summary statistics will be provided by dose level (see [Table 1-2](#)) and sampling time point. Summary statistics will include mean (arithmetic and geometric), SD, CV (arithmetic and geometric), median, minimum, maximum, and the frequency (n, %) of concentrations below the LLOQ. Concentrations below LLOQ will be treated as zero in summary statistics and for PK parameter calculations. A geometric mean will not be reported if the dataset includes zero values. For all doses, the unit is transferred from “mg/m²” to “mg/kg” for summary statistics calculation. The summary statistics table also include columns with treatment group in Parts 2 & 3. A geometric mean will not be reported if

the dataset includes zero values. Graphical methods will be employed to show mean and individual concentration-time profiles. Pharmacokinetic parameters will be listed by study part, administered dose and subject and summarized by dose with descriptive summary statistics as described above. An exception to this is Tmax where median, minimum and maximum will be presented.

2.9.2 Accumulation ratio

Part 1

In subjects, who received the same dose in the first two treatment cycles of 3 months each, the parameters AUC0-168h for both observations and Cmax will be log transformed and used in an ANCOVA model with day as a factor, log dose as a covariate and day by dose interaction and subject as random effect. The LSMeans and their mean difference between treatment cycle 2 and Day 1 for each dose level, together with 90% confidence limit will be calculated from this model. These will be back-transformed to provide an estimate of the accumulation ratio with corresponding 90% CI.

Part 2

Accumulation ratio can be estimated as described for Part 1. Since no intra-individual dose escalation is planned, the accumulation will be estimated for each observation period versus first administration.

